6.3. Definition of Analysis Timepoints

- **Baseline:** The last non-missing observation (including unscheduled visits) prior to the first dose of study drug (cytisinicline and/or placebo), unless otherwise specified. The last non-missing observation prior to the first dose of study drug (cytisinicline and/or placebo), unless for randomized subjects who do not receive study drug then baseline is defined prior to date of randomization. If both a planned assessment and repeat assessment (eg, retest) meet the above criteria and were collected on the same date and time, the repeat assessment will be used as baseline.
- **Change from Baseline:** The change from baseline values will be derived for each subject as the post-baseline value minus the baseline value.
- **End of Treatment (EOT) Visit:** The last clinic visit during the treatment period. Expected to occur at Week 12 (Day 86/EOT visit) for subjects who complete the 12-week treatment period. Subjects who discontinue treatment prior to 12 weeks will have the EOT visit when treatment is discontinued. (See Section 4.2.1.4.)
- **Pre-treatment Period:** Prior to first dose of study drug on Day 1.
- **Treatment Period:** The treatment period is expected to be 84 days (12 weeks) in duration. For an individual subject, the treatment period starts on the date of the first dose of study drug (Day 1), continues through the date of the last dose of study drug, and ends on the date of the Week 12 (Day 86/EOT) visit.
- **Follow-up Period:** The follow-up period is expected to be 12 weeks in duration, and includes the monthly visits at Week 16, Week 20, and Week 24.
- **Study Day:** Study day will be calculated for all assessment dates relative to the first dose of study drug (cytisinicline and/or placebo). The first dose of study drug will be Day 1, and the date preceding Day 1 will be Day –1 which is consistent with the Submission Data Standards (Version 3.1) from Clinical Data Interchange Standards Consortium (CDISC).

6.4. Data Handling Rules

Dropouts (ICH E3/11.4.2.2) will not be replaced during the study, but will be included in the data analysis to the extent that evaluable data are present.

For qualitative parameters, a category with the number of subjects with missing values will be presented where applicable.

6.4.1. Missing Dates

Partial or missing dates will be imputed only if a date is required to derive a study endpoint (eg, time to failure, duration of AE) or a variable used in study analyses. Otherwise no date imputation will be done. Date imputation will follow the rules below.

Efficacy Related Dates

Partial or missing dates required to compute efficacy endpoints will be imputed as follows:

- Missing day only: For partial dates with only the day of the month missing, the day will be imputed as the 15th day of the month, provided that a preceding date of interest does not occur in the same month. If the preceding date does occur in the same month, then the missing day will be imputed as half the distance between the preceding date and the end of the month. For example, if the Week 2 visit occurs on the 15th day and Week 3 day was missing, Week 3 day could not be day 15, it would be day 22.
- Missing month and day: For partial dates with the month and day missing, the month and day will be imputed as July 1st, provided that a preceding date of interest does not occur in the same year. If the preceding date occurs in the same year, then the month and day will be imputed as half the distance from the preceding date to the end of the known year.
- Missing month, day, and year: Missing dates will be imputed as the date of first dose.
- In situations where the above rules result in an illogical time (eg, negative study day, negative time to failure, etc) the date will be imputed as the date half the distance between the preceding date of interest and the partial date.

Safety Related Dates

For medications occurring prior to first dose of study drug. Missing or partial date will not be imputed. For safety data besides medications where the date of onset is during or after administration of the first dose of study drug, missing or partial start dates will be imputed as the earliest possible date that is on or after the date of the first dose of study drug. For events occurring prior to first dose of study drug, missing or partial dates will not be imputed.

- Missing day only: If the start date and date of first dose share the same month and year, the missing start day will be imputed as the day of first dose. If the start date month is after the month of first dose, day will be imputed as the 1st (ie, 01-Jan-2019).
- Missing month only: If the start date and date of first dose share the same year, month will be imputed as the month of the first dose. If the start date year is after the year of the first dose, the month will be imputed as Jan.
- Missing month and day: If the start date and date of first dose share the same year, day and month will be imputed as the day and month of first dose. If the start date year is after the year of first dose, the month and day will be imputed as January 1st (ie, 01-Jan-2019).

- Missing month, day, and year: Missing start dates will be imputed as the date of first dose.
- For partial end dates: Missing month and day: if year matches the year of the last date of study (date of last contact if subject lost to follow-up; date of completion or early termination), then impute as the month and day of the last date of the study, otherwise assign 31-December.
- Missing month only: if year matches the year of the last date in the study (date of last contact if subject lost to follow-up; date of completion or early termination), then impute as the month of the last date of the study, otherwise assigned December.
- Missing day only: if the month and year match the month and year of the last date of study, then impute as the day of the last date of the study; otherwise assign the last day of the month.

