Time to failure to maintain abstinence will be evaluated for the subset of subjects who were classified as a success for abstinence at Weeks 3-6. Time to failure to maintain abstinence (days) will be calculated as end date of abstinence minus start date of abstinence +1. The start date of abstinence will be defined as the date of the Week 6 visit. The end date of abstinence will be defined as the earliest date that the subject was known to have resumed smoking, or will be censored, as described below:

- At a visit during the treatment period, if a subject reported smoking since the last visit (either by the subject's self-report or CO ≥ 10 ppm), the end date of abstinence will be the earliest of the following dates: the date the subject reported resuming smoking, or the date of CO ≥ 10 ppm.
- During the follow-up period, if a subject reported smoking a total of more than 5 cigarettes at the attended Week 16, Week 20, and Week 24 visits, or CO ≥ 10 ppm at a visit, the end date of abstinence will be the earliest of the following dates: the date the subject reported smoking the 6th cigarette, or the date of CO ≥ 10 ppm.
- Subjects who have not resumed smoking at their final visit will have end date of abstinence censored at the date of that final visit. (The final visit is expected to be the Week 24 visit.)

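### SAP 6.4.1 does not bound an imputed date of resumed smoking by the visit that reported it, so partial dates can put a relapse days to months after that visit in the exploratory time-to-failure analysis

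*SAP*

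**What the plan says.** SAP 6.4.1 (Missing Dates) limits imputation to where it is needed: "Partial or missing dates will be imputed only if a date is required to derive a study endpoint (eg, time to failure, duration of AE". Time to failure is therefore an endpoint that these rules are meant to serve. For efficacy dates:

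- **Day missing, preceding date in an earlier month:** it "will be imputed as the 15th day of the month, provided that a preceding date of interest does not occur in the same month".
- **Day missing, preceding date in the same month:** "the missing day will be imputed as half the distance between the preceding date and the end of the month". The SAP illustrates this with a Week 2 visit on day 15: "Week 3 day could not be day 15, it would be day 22".
- **Month and day missing, preceding date in an earlier year:** "the month and day will be imputed as July 1st, provided that a preceding date of interest does not occur in the same year".
- **Month and day missing, preceding date in the same year:** "the month and day will be imputed as half the distance from the preceding date to the end of the known year".
- **Fallback:** it opens "In situations where the above rules result in an illogical time (eg, negative study day, negative time to failure, etc", and then halves the distance from the preceding date to the partial date.

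SAP 4.1.3 starts the clock at the Week 6 visit. During treatment it ends abstinence at "the earliest of the following dates: the date the subject reported resuming smoking" or the date of CO of 10 ppm or more. In follow-up, the date of the 6th cigarette takes the place of the resumption date.

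**The concern.** Smoking is reported at a clinic visit as having happened since the last one (Protocol 12.2.3 and 12.2.4). A reported relapse therefore lies between two known dates: 7 days apart at most treatment visits, 9 days from Day 77 to Day 86, and about 28 days in follow-up (Protocol, Section 12). The imputation rules use the first of these dates and ignore the second. They can date a relapse after the subject has already reported it, and in some cases after the Week 24 visit.

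At stake is the time-to-failure analysis (Other Objective 9; SAP 10.2.8). Where dates are partial, its Kaplan-Meier curves would stay up longer than the data allow. In the same SAP section, the safety end-date rules are tied to the subject's last study date when the known parts match, so the missing bound looks like an oversight.

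**Working it through.** **The SAP's own example.** Preceding visit on day 15, month of length L: 15 + (L − 15)/2. For L = 30 this is 22.5, rounded down to 22; for L = 29 it is 22. The stated day 22 is reproduced. (L = 28 gives 21 and L = 31 gives 23.)

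**Three illustrative records, before any CO reading is used.**

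1. Week 6 visit 3 March 2022, smoking reported at Week 7 on 10 March, day missing. From 3 to 31 March is 28 days; half is 14; the imputed date is 17 March, 7 days after the report.
2. Visits 28 February and 7 March, month known to be March, day missing. The imputed date is 15 March, 8 days after the report.
3. As record 1, but only the year is known. From 3 March to 31 December is 303 days; half is 151 (rounded down); the imputed date is 1 August. Time to failure is 151 + 1 = 152 days, when the true value is at most 7 + 1 = 8. Week 24 is Week 6 + 126 days = 7 July, so the event falls 25 days after it.

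**Enumeration.** Assumptions: the previous visit falls on each of 365 calendar dates; the relapse falls on each day after it up to the reporting visit, with equal weight; half-days are rounded down. The table gives the share of imputed dates later than the reporting visit.

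| Missing part | Preceding date read as | Weekly visits | Four-weekly visits |
|---|---|---|---|
| Month and day | Previous visit | 96.7% (mean excess 89 days) | 88.1% (mean excess 81 days) |
| Day only | Previous visit | 60.5% (mean excess 5.4 days) | 12.3% (mean excess 5.3 days) |
| Month and day | Week 6 visit | 87–95% | 61–77% |
| Day only | Week 6 visit | 36–38% | 12–13% |

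Under the previous-visit reading the largest excess is 181 days (month and day) and 14 days (day only). With gaps of 6 to 10 days the day-only share runs from 65.5% to 45.8%; with gaps of 21 to 35 days, from 16.4% to 9.9%.

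Pooled over both visit spacings, day-only dates fall late more than half the time only if the weekly share w satisfies 0.605w + 0.123(1 − w) > 0.5, that is, w above 0.78.

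**CO rule.** Let c be the share of reporting visits with CO of 10 ppm or more. The documents do not give it, so its range is 0 to 1. Each share in the table is multiplied by (1 − c). At c = 0.5, under the previous-visit reading, the month-and-day shares are 48.4% and 44.0%, and the day-only shares 30.3% and 6.2%. A CO of 10 ppm or more at a later visit before the imputed date shortens the excess further.

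**Fallback read broadly.** Suppose its open-ended list also covers dates after the reporting visit. Under the previous-visit reading, the day-only shares fall to 9.9% (weekly) and 0% (four-weekly). The month-and-day shares stay at 92.3% and 72.2%. Record 3 would move to 3 March + 75 days = 17 May, still 68 days after the report.

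**The case against.** The strongest reply has four parts.

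*The CO rule already limits the error.* This stands in part. SAP 4.1.3 takes the earliest date with no same-visit restriction, so any CO of 10 ppm or more before the imputed date takes over. Record 3 needs CO below 10 ppm, or missing, at every visit from Week 7 to Week 24. But self-report alone counts as relapse, so a subject who reports smoking with CO below 10 ppm at that visit is not protected there.

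*The records may be rare or may not arise.* This stands as an unknown. The visit questions in Protocol 12.2.3 and 12.2.4 ask whether and how much the subject smoked, and list no resumption date. SAP 4.1.3 assumes one exists, but the eCRF is not available. Protocol 19.2 sends incomplete entries to query, and a year-only entry for an event since the last visit would be unusual. If no date is collected, the rule for fully missing dates applies, which is a different matter.

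*The fallback may catch these dates.* Its examples are all negative times, whereas these are positive. Read broadly, it largely repairs the day-only rule. It repairs the month-and-day rule only where the preceding date is also read as Week 6 and the relapse comes late: on both readings together, the late share runs from 87% at Weeks 7–8 down to 11% at Weeks 20–24.

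*The consequences are small.* This stands. SAP 10.2 labels the analysis exploratory, and 10.2.8 plans descriptive statistics and a figure, with no test named.

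A reader might infer that partial relapse dates in general are usually placed too late. The documents do not support that: a missing day at four-weekly visits does so about 12% of the time, and at weekly visits the share drops below 40% if the preceding date is Week 6. A reader might also infer bias in the efficacy conclusions or between arms. The binary primary and secondary endpoints use no relapse date, the same rules apply to every arm, and nothing in the documents shows that partial dates differ by arm.

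**Conclusion.** The point holds as a gap in the rules: nothing in SAP 6.4.1 stops an imputed date of resumed smoking, or of the 6th cigarette, from falling after the visit that reported it. The month-and-day rule does this in most cases under either reading of the preceding date (61–97% before the CO rule), by weeks to months. The day-only rule does it by days, and its frequency depends on visit spacing and on a term the SAP leaves undefined.

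The overstatement is largest for self-reported relapses with no CO of 10 ppm or more up to the imputed date. All shares are per partial date and rest on equal weighting over calendar and relapse days. The number of partial dates and the CO-positive share are unknown, so the effect on the curves cannot be sized. The matter is minor and worth correcting because the correction is easy.

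**What to change.** In SAP 6.4.1, keep the existing bullets for other efficacy dates (the SAP's own example is a visit date, which still needs a rule), define *preceding date of interest*, and add:

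> A partial date of resumed smoking or of the 6th cigarette is imputed as the midpoint between the previous attended visit and the visit at which the smoking was reported, restricted to days consistent with the known month and year, and is never later than the reporting visit.

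Before the CO rule and under the previous-visit reading, a cap at the reporting visit alone would cut the mean error for month-and-day dates from +88.8 to +2.9 days (weekly) and from +83.7 to +12.2 days (four-weekly). For day-only dates it would go from +5.2 to +2.0 and from +2.0 to +1.4 days. A midpoint between the visits, cut at month end where that comes first for a missing day, gives mean errors of about −0.5 to −2.8 days.

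The cost is a sentence and a definition in the SAP, and a small change to the derivation code. The visit dates needed are already collected.

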7. Provide subject with behavioral support information that includes counseling ([Appendix 7](#)). NOTE: Again it should be stressed to subjects that they must maintain their dosing schedule throughout the Treatment Period and to be honest with their smoking status information.
8. Blood for hematology, serum chemistry and cotinine testing.

9. 12-lead ECG.
10. Expired CO.
11. Record the following:
 - a. Has the subject smoked any cigarettes since the last clinic (Day 35) visit?
 - b. If subject has smoked, subject should report the total number of cigarettes smoked since the last visit.
 - c. Has the subject used any non-cigarette nicotine products, including vaping, since the last clinic (Day 35) visit? If yes, record what was used and remind subject such products should not be used during the study.
12. Remind subject of their Day 49 (Week 7) appointment date and time and that they must bring with them their study treatment packs.

Treatment Day 49/Week 7 (± 1 day)

1. Subject to complete the MNWS questionnaire ([Appendix 5](#)).
2. Review study treatment diary to verify dosing up to time of visit.
3. Assess for AEs and any changes to concomitant medications.
4. Vital signs, including weight.
5. Review study treatment Week 7 pack for compliance and collect the Week 6 pack (which was the last pack in Carton #1 and should be empty if all doses were taken as expected). Retain Carton #1 and all weekly packs for drug accountability by the study monitor. Confirm that the subject has the Week 8 pack and provide a study treatment Week 9 pack from Carton #2.
6. Provide subject with behavioral support information that includes counseling ([Appendix 7](#)). NOTE: Again it should be stressed to subjects that they must maintain their dosing schedule throughout the Treatment Period and to be honest with their smoking status information.
7. Expired CO.
8. Record the following:
 - a. Has the subject smoked any cigarettes since the last clinic (Day 42) visit?
 - b. If subject has smoked, subject should report the total number of cigarettes smoked since the last clinic visit.
 - c. Has the subject used any non-cigarette nicotine products, including vaping, since the last clinic (Day 42) visit? If yes, record what was used and remind subject such products should not be used during the study.
9. Remind subject of their Day 56 (Week 8) appointment date and time and that they must bring with them their study treatment packs.

Treatment Day 56/Week 8 (±1 day)

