12.2.4. Follow Up Period for Smoking Cessation Assessments

Week 16 (± 1 week)

1. Record the following:
 - a. Has the subject smoked any cigarettes since the last (Day 86/Week 12) clinic visit?
 - b. Has the subject smoked any cigarettes over the past 7 days?
 - c. If subject has smoked, subject should report the total number of cigarettes smoked.
 - d. Has the subject used any non-cigarette nicotine products, including vaping, since the last clinic (Day 86/Week 12) visit? If yes, record what was used and remind subject such products should not be used during the study.
2. Assess for AEs.
3. Blood for cotinine testing.
4. Expired CO.
5. Provide subject with abbreviated behavioral support based on issues/concerns/questions raised ([Appendix 7](#)).
6. All subjects regardless of smoking status are to be scheduled for their Week 20 (± 3 days) follow-up visit.

Week 20 (± 1 week)

1. Record the following:
 - a. Has the subject smoked any cigarettes since the last clinic (Week 16) visit?
 - b. Has the subject smoked any cigarettes over the past 7 days?
 - c. If subject has smoked, subject should report the total number of cigarettes smoked.
 - d. Has the subject used any non-cigarette nicotine products, including vaping, since the last clinic (Week 16) visit? If yes, record what was used and remind subject such products should not be used during the study.
2. Assess for AEs.
3. Blood for cotinine testing.
4. Expired CO.

5. Provide subject with abbreviated behavioral support based on issues/concerns/questions raised ([Appendix 7](#)).
6. All subjects, regardless of their smoking status, should be scheduled for their Week 24 (± 3 days) follow-up visit.

Week 24 (± 1 week)

1. Record the following:
 - a. Has the subject smoked any cigarettes since the last clinic (Week 20) visit?
 - b. Has the subject smoked any cigarettes over the past 7 days?
 - c. If subject has smoked, subject should report the total number of cigarettes smoked.
 - d. Has the subject used any non-cigarette nicotine products, including vaping, since the last clinic (Week 20) visit? If yes, record what was used and remind subject such products should not be used during the study.
2. Assess for AEs.
3. Blood for cotinine testing.
4. Expired CO.
5. Provide subject with abbreviated behavioral support based on issues/concerns/questions raised ([Appendix 7](#)).
6. Discharge subject from study.

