10.2.8. Time to Failure to Maintain Abstinence

Time to failure to maintain abstinence will be evaluated for the subset of subjects who were classified as a success for abstinence from Week 3 to Week 6. Time to failure (days) will be calculated for individual subjects as described in Section 4.1.3. Subjects who are still abstinent at Week 24 will have time to failure censored at the date of the Week 24 visit.

Time to failure will be summarized by treatment arm; the minimum, maximum, median and 95% confidence interval for the median time to failure reported by the LIFETEST procedure will be reported. A Kaplan-Meier figure of treatment arm by time to failure will be produced.

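### For the exploratory time-to-failure summary, SAP 6.4.1 places a wholly missing relapse date about 40 days before the clock starts, and its fallback gives no usable date

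*SAP*

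**What the plan says.** SAP 6.4.1 (Missing Dates) opens by limiting its scope. Dates are "imputed only if a date is required to derive a study endpoint (eg, time to failure, duration of AE"), so time to failure is the first endpoint it names. The efficacy-related rules then cover a missing day, a missing month and day, and a date missing altogether: "Missing month, day, and year: Missing dates will be imputed as the date of first dose". A last bullet covers results that make no sense, with negative time to failure among its examples. In that case, "the date will be imputed as the date half the distance between the preceding date of interest and the partial date".

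SAP 4.1.3 defines the endpoint, only for subjects classified as abstinent at Weeks 3-6, as end date minus start date plus 1. "The start date of abstinence will be defined as the date of the Week 6 visit". During treatment the end date is the "earliest of the following dates: the date the subject reported resuming smoking, or the date of CO" at or above 10 ppm. In follow-up it is the earlier of the date of the sixth cigarette and the date of such a CO reading. SAP 10.2.8 adopts this: "Time to failure (days) will be calculated for individual subjects as described in Section 4.1.3". It reports the minimum, maximum, median with its confidence interval, and a Kaplan-Meier figure by arm.

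The Protocol's visit lists record whether the subject smoked and how much. From Week 2 to Week 12 the "subject should report the total number of cigarettes smoked since the last clinic visit"; at Weeks 16 to 24, "If subject has smoked, subject should report the total number of cigarettes smoked". Neither list asks when smoking resumed or when the sixth cigarette was smoked. The smoking diary is for screening only, and the on-study diary records dosing (Protocol 12.2.5).

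**The concern.** First dose is a poor stand-in for a relapse date when the clock starts six weeks later. Everyone in this analysis was verified abstinent at the Week 6 visit: SAP 4.1.1 counts unknown status at Week 6 as failure and otherwise requires a report of no smoking with CO below 10 ppm. An imputed relapse at Day 1 therefore contradicts the condition for entering the analysis.

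The SAP authors foresaw a negative time, so the question is whether their fallback repairs it. If it does not, an affected subject has an impossible time, no defined date, or a relapse date earlier than a visit at which abstinence was verified. The programmer would then have to invent a rule for a summary that the SAP appears to have specified.

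**Working it through.** **The SAP's own example.** 6.4.1 illustrates the half-distance idea: with the preceding date on the 15th, a missing day becomes day 22. With L days in the month, 15 + (L − 15)/2 gives 22.0 for L = 29, 22.5 for L = 30 and 23.0 for L = 31. Day 22 is reproduced exactly for 29 days and by truncation for 30. No rounding rule is stated.

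**Inputs.** First dose is Day 1 (SAP 6.3). Visit days for Weeks 6 to 12 are 42, 49, 56, 63, 70, 77 and 86, each ± 1 day (Protocol 12 and Table 4). For Weeks 16, 20 and 24 I use 7 × week = 112, 140 and 168. Time = end − start + 1 (SAP 4.1.3).

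**Rule for a wholly missing date.** Time = 1 − 42 + 1 = −40 days. With Week 6 on Day 41 or 43 it is −39 or −41.

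**Fallback read literally.** It is triggered, because the time is negative. It then asks for the midpoint between a preceding date of interest and the partial date. The first term is not defined, and a wholly missing date has no partial date, so no date results.

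**Fallback on one assumed reading.** Let the imputed Day 1 stand in for the partial date, and let the last abstinent visit, Day P, be the preceding date of interest. Neither choice is SAP text. Then end = (P + 1)/2 and time = (P + 1)/2 − 41. The last two columns show alternatives for comparison, with D the next scheduled visit: the midpoint, (P + D)/2 − 41, and the detection visit itself, D − 41.

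| Last abstinent visit | P | (P + 1)/2 | Time | Days before visit P | D | Midpoint time | Detection-visit time |
|---|---|---|---|---|---|---|---|
| Week 6 | 42 | 21.5 | −19.5 | 20.5 | 49 | 4.5 | 8 |
| Week 7 | 49 | 25 | −16 | 24 | 56 | 11.5 | 15 |
| Week 8 | 56 | 28.5 | −12.5 | 27.5 | 63 | 18.5 | 22 |
| Week 9 | 63 | 32 | −9 | 31 | 70 | 25.5 | 29 |
| Week 10 | 70 | 35.5 | −5.5 | 34.5 | 77 | 32.5 | 36 |
| Week 11 | 77 | 39 | −2 | 38 | 86 | 40.5 | 45 |
| Week 12 | 86 | 43.5 | 2.5 | 42.5 | 112 | 58 | 71 |
| Week 16 | 112 | 56.5 | 15.5 | 55.5 | 140 | 85 | 99 |
| Week 20 | 140 | 70.5 | 29.5 | 69.5 | 168 | 113 | 127 |

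On this reading the time is positive only when P > 81. With Week 6 on Day W the condition is P > 2W − 3, that is 79, 81 or 83 for W = 41, 42 or 43. Week 11 falls no later than Day 78 and Week 12 no earlier than Day 85, so the change of sign lies between those two visits whatever the window. The positive values are no better: each places relapse 42.5 to 69.5 days before a visit at which the abstinence criteria were met, and a check for negative times would not catch them.

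**The case against.** The strongest reply is that the problem may never arise. The phrase in 4.1.3 about the date on which resumed smoking was reported can be read as the date of the visit at which smoking was reported. That fits what the visits collect, and it fits the follow-up wording, which speaks of cigarettes reported at attended visits. On that reading the end date is a visit date and is unlikely to be wholly missing. The only worked example in 6.4.1 is itself a missing visit day. This stands as a limit: the point needs a separate resumption or sixth-cigarette date. The eCRF and Data Entry Guidelines, which the SAP cites but which are not among the documents, would settle whether one is collected.

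Four stronger readings are tempting and are not supported.

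- A reader might infer that −40 days would enter the Kaplan-Meier estimate. 6.4.1 names negative time to failure and replaces the date, so −40 is the output of the first rule, not a value that would be analysed as such.
- A reader might take the fallback times in the table as the SAP's results. They depend on the assumed reading. If the reporting visit supplied the later date, the same sentence would give the ordinary midpoint between visits.
- A reader might infer that an imputed Day 1 beats an observed CO date, because 4.1.3 takes the earliest date. But 6.4.1 imputes only dates that are required, and 4.1.3 speaks of the earliest date on which smoking was known to have resumed. Where a CO date exists, an end date exists already.
- A reader might infer from the visit lists that such dates will often be missing. The Protocol does not show everything the eCRF collects, so no frequency can be given.

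**Conclusion.** The point holds, as a minor one. For a wholly missing relapse date, 6.4.1 states a rule that gives −40 days (−39 to −41), and the fallback meant to catch this lacks one of its two inputs. Read literally it gives no date. With Day 1 put in for the missing input, it gives a negative time for a last abstinent visit at Weeks 6 to 11, and a relapse date before verified abstinence from Week 12 on. This is a stated rule that fails, not merely a missing detail.

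Its reach is small. It affects only subjects for whom a separate resumption or sixth-cigarette date is needed and is wholly missing, mainly those who report smoking with CO below 10 ppm. Their number could be zero. The table assumes nominal visit days and no missed visits. The endpoint is exploratory (SAP 10.2), and 10.2.8 plans only a descriptive summary without a test. The primary and secondary endpoints are visit-based classifications, so their inference is unaffected.

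**What to change.** In SAP 6.4.1, exempt time to failure from first-dose imputation and add a short rule:

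- Where an observed CO of 10 ppm or more, or a reported date, gives the end date under 4.1.3, use it and impute nothing.
- Otherwise place a wholly missing date between the last visit meeting the 4.1.3 abstinence criteria and the visit at which failure was first reported. Either the midpoint, with a stated rounding rule for half days, or the detection-visit date would serve; choose one in advance.
- Never impute a date before a visit with verified abstinence.

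It would also help to say in 4.1.3 whether the reported resumption date means the reporting visit or a recalled calendar date.

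The cost is two or three sentences and one derivation, with no new data. The downside is that the imputed date is approximate. The uncertainty is about a week during treatment and about 4 weeks in follow-up, where the choice between midpoint and detection visit moves the time by 13 or 14 days (71 − 58 = 13; 99 − 85 = 14; 127 − 113 = 14).
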